#### **1.4.1 PRECLINICAL STUDIES WITH ICG**

Similar to animal studies with Fluorescein, ICG has been used to study blood flow in several different models.[60-62] ICG has been successfully used in these studies to characterize the vasculature associated with the tumor microenvironment.

#### **1.4.2 CLINICAL STUDIES WITH ICG**

Similar to Fluorescein, ICG is not expected to have a direct intervention on tumor biology. ICG has been used during the course of surgery and other procedures for widespread indications and is FDA approved. In general, it is well tolerated, non-toxic, and has no long term side effects.

Clinically, ICG is most commonly used in the assessment of liver function,[63-65] ophthalmic angiography,[66-68] and the analysis of cardiac function with increasingly novel applications in cardiac studies.[69, 70] It is typically administered by a member of the anesthesia team during cases or procedures in the operating suite under general anesthesia. In addition to these applications, ICG has been used in a variety of other studies in a safe manner. ICG has been used to map sentinel lymph nodes (SLN) in several malignancies,[71] including melanoma,[56, 72, 73] breast,[74-76] and colon cancer.[77] These studies have not reported any major adverse reactions or toxicities resulting from exposure to ICG. While the doses of ICG used in these studies varies, the recommended dose per the manufacturer is calculated on the basis of 0.5 mg/kg of body weight.[55]

Other applications of ICG have been studied in the field of plastics surgery. ICG has been given in patients to determine the perfusion and viability of perforator flaps.[78, 79] Similar to the studies in malignancy and SLN, the fluorescent properties of ICG have been utilized and shown to be effective in other studies. ICG has also been used to identify and target esophageal varices.[80] Further, during neurovascular operations, ICG has been readily administered by

anesthesiologists during intraoperative videography of aneurysm clippings and carotid bypass procedures.[81, 82]

As discussed in the previous section, the use of ICG is contraindicated in patients with a history of allergic hypersensitivity to iodine. There have been rare but reported cases of anaphylaxis and death due to allergic reactions during procedures using ICG.[25, 83, 84] Therefore, patients with a history iodine allergy will be excluded from our clinical trial. Other adverse reactions have been reported with the use of ICG in patients with allergic reactions.[85]

A higher risk of adverse reactions has been reported in small studies in patients with liver disease, chronic kidney disease, and uremia.[84] Although the manufacturer does list these conditions as contraindications, patients with uremia or liver disease will be identified through a thorough history and physical, and screened with a basic metabolic panel (which includes a serum creatinine and blood urea nitrogen or BUN) and liver function tests (LFT's). These patients will be informed of the potential increased risk for side effects and may be excluded from the study.

The safety of ICG has been assessed in pregnancy, although there exist no strong level of evidence (i.e. randomized controlled trials) to determine conclusively the safety of ICG in pregnant patients. As such, it is labeled by the FDA as pregnancy category C. There do exist retrospective series and case reports that have safely utilized ICG in the pregnant patient. ICG has been used in the study of ophthalmic angiography during preeclampsia.[86] A survey of ophthalmologists who use ICG in the study of retinal vessels showed that 89% of the surveyed ophthalmologists have encountered at least one pregnant patient who required either ICG or Fluorescein angiography, and of these 24% withheld ICG angiography.[87] Regarding nursing mothers, it is unknown where ICG is excreted in human milk and can have any adverse effects in the newborn or infant period. Due to the limited data, pregnant and nursing mothers will be excluded from the trial in a similar manner with regard to the use of Fluorescein. A routine day of surgery pregnancy test is performed for pre-menopausal patients.

Historically, the rate of adverse reactions to ICG are low. A study of over 1900 cases of ICG video angiography cases in the ophthalmologic setting reported the incidence of mild, moderate and severe reactions to be 0.15%, 0.2% and 0.05%, respectively.[84] ICG was administered IV in these cases. The death rate after ICG injection has been cited as 1 in 333,333.[84]

Transient nausea and vomiting, and local discomfort, are the most common reactions and require no treatment. These mild reactions typically occur shortly after injection and are transient.[84]

Moderate reactions such as pruritus or urticaria can be treated with antihistamines, but any patient who experiences these symptoms will be observed carefully for the possible development of anaphylaxis. These symptoms have been successfully treated with antihistamines, and were of short duration.[84] In the event of severe reactions, assessment and treatment will be implemented similar to protocol used in Fluorescein adverse reactions.

Severe reactions include anaphylactic reactions. The dose of ICG has not been well correlated to the severity of symptoms. These symptoms include severe generalized pruritis, diaphoresis, weakness, agitation, and syncope.[84, 88] Signs include hypotension and hemodynamic instability. In extreme cases, death may result. Although life-threatening reactions during angiography are rare, angiographic facilities and personnel should be properly equipped and prepared to manage serious reactions to the procedure. A resuscitative crash cart and appropriate agents to treat severe reactions will be readily available (including epinephrine for intravenous or intramuscular use, soluble corticosteroids, aminophylline for intravenous use, oxygen, and airway instrumentation). It is generally recommended that a physician be present or available during angiographic procedures.

Local toxicity has been described for ICG, but largely in the setting of topical application during ophthalmologic procedures.[89, 90] ICG has widespread use as a vital stain during macular surgery. It is hypothesized that the local irritant effects combined with the hypo-osmolar tonicity over prolonged exposure times (over 10 minutes) may contribute to local toxicities to the macula, potentially resulting in decreased visual acuity, optic disc changes, and visual field deficits.[91] However, in our application of ICG for HIVM, local effects should be minimized through IV injection and dilution as it enters the blood stream. These toxicities have not been reported in studies where ICG has been used intravenously for liver and cardiac function. Mild discomfort has been associated with extravasation.[84] Care will be taken to minimize injection within the soft tissue and limit extravasation of ICG.

## 1.5 RISKS AND/OR BENEFITS

**Risks** – similar to the section on fluorescein, low risk of reaction to ICG as described above. Otherwise, no increased risk to the surgical procedure anticipated.

**Benefits** – depending upon collected findings and correlation with clinical outcome, IVM may offer prognostic information and improve the staging classification of peritoneal tumors with the intent of potentially guiding treatment decisions in the future.

## 2 RATIONALE

These studies will elucidate the hemodynamic properties of microvessels associated with peritoneal carcinomatosis. In order to model the effects of tumor-associated vessel function on patient outcomes, direct examination of the microvasculature in these patients is necessary to ascertain if the preclinical model systems have accurately recapitulated the clinical setting. Thus, the current proposed trial represents an opportunity to support the development of interventions to improve patient treatment by extending the application of IVM to the locoregional tumor microenvironment.

### 3 OBJECTIVES

#### 3.1 PRIMARY OBJECTIVE - PART I (10 PATIENTS):

To determine the feasibility of performing HIVM in patients with peritoneal carcinomatosis during standard course of treatment (cytoreductive surgery with hyperthermic intraperitoneal chemotherapy, or CRS-HIPEC). A successful intravital microscopic observation will include the ability to complete each of the following:

1. Identify and measure vessels associated with peritoneal tumor implants
2. Determine vessel density per 10x field
3. Visualize vital dyes within the vessels [fluorescein and indocyanine green (ICG)]
4. Calculate the blood flow velocity of the vessels and tissue penetration of fluorescein and ICG as markers of vessel permeability.

#### 3.2 SECONDARY OBJECTIVES - PART II (20 PATIENTS):

1. Compare the microscopic observation of the tumor-associated vessels with normal tissue (peritoneal surface) in each individual subject.
2. Correlate the microscopic observations of the tumor-associated vessels with pathologic grade of tumor implants.
3. To correlate the microscopic observation of the microvasculature with tumor-specific and overall survival.

#### 3.3 PRIMARY AND SECONDARY ENDPOINTS:

*Primary endpoint:* A patient will be deemed a success if each of the following parameters were measured:

1. Identify tumor implant associated vessels and measure vessel diameters
2. Determine vessel density per 10x field
3. Visualize vital dyes within the tumor-associated vessels (fluorescein and green ICG)
4. Calculate the blood flow velocity of the tumor-associated vessels and tissue penetration of fluorescein and ICG as markers of vessel permeability.

*Secondary endpoints:*

1. Post-operative comparison of the microvasculature of peritoneal carcinomatosis with normal tissue (peritoneum) in each individual subject using vessel diameters, vessel density, detection of intravital dye and flow rates.
2. Post-operative correlation of the microvasculature with pathologic features of the tumor implants (i.e. tumor grade) at the time of the final pathology report (5-7 days after surgery).

3. Post-operative correlation of the microscopic observation of the tumor microvasculature tumor-specific and overall survival.

## 4 METHODOLOGY

### 4.1 Study Design

This is an open-label, non-randomized, single center, study of IVM observation in conjunction with fluorescein and ICG in subjects with peritoneal carcinomatosis undergoing CRS-HIPEC. The first part is a Pilot study of feasibility.

Subjects will be treated on an inpatient basis. All subjects will meet the inclusion and exclusion criteria summarized in **Section 5.1** and **Section 5.2** prior to participation in this study. Standard evaluation by the Preoperative Anesthesia clinic may include additional testing such as EKG, chest x-ray, and/or pulmonary function tests, but this is performed based upon their established guidelines. If any of these tests preclude a wide excision in the operating room, then the patient is excluded from this study.

### 4.2 STUDY METHODS

During the course of treatment for peritoneal carcinomatosis while the patient is under anesthesia, CRS-HIPEC will be performed. Surgical exposure is performed through a midline incision and the assistance of retractors as shown in the technical schema (Appendix D).

The IVM technology utilized at Mayo Clinic currently consists of a high resolution confocal endomicroscope (Appendix E). This apparatus has the ability to provide single cell resolution and high quality images of the microvasculature. While the typical application of this device is to investigate GI mucosal surfaces (i.e. esophagus or colon), it can be readily and easily applied to any surface. It can be sterilized or used with a sterile sleeve in order to interface with the peritoneal surface.

The microscope will be moved into position next to the OR table by the operating surgeon. The microscope will be covered with a standard sterile drape similar to that used for cords associated with other intraoperative devices (NeoProbe or intraoperative ultrasound). The only exposed area will be the microscopic objective located at the tip of the endoscope, which will be made sterile. This microscopic objective will come into close contact with the peritoneal surface for microscopic observation. Once the microscopic objective is in proper position, the epifluorescent light source will be turned on and digital video recording will commence. All video images will be captured to the hardware directly attached to the microscope (Appendix E). All data will be backed up on a password-protected hard drive in the Principal Investigator's laboratory.

Following several observations over various portions of the peritoneal surface, 1 ampule (5 mL) 25% fluorescein will be injected intravenously and observation will continue until loss of

fluorescence. IVM is continuously performed at the time the fluorescent agent is injected and video is recorded in real-time. The fluorescein is almost immediately visible within the microscopic field, and the vessels are quickly outlined in great detail. The fluorescence lasts for a few minutes (2-3 minutes) and then either fades or begins to permeate through the tissue. The extravasation of dye will be determined by visualizing fluorescence outside of the defined vessels for a total time of 5 minutes. The distance from the vessels will be measured, recorded, and expressed as a function of time (extravasation rate) in an analysis performed off-line from the digitally recorded video.

Following the dissipation of the fluorescein from the visual field, 5 mg of ICG will be injected intraveneously. The observation will repeat in a similar manner, now with the use of ICG. Tumor-associated vasculature will be observed in order to record the similar vessel characteristics. ICG is expected to persist within the vasculature for an extended period of time, thereby allowing further characterization of the field. It is not necessary to wait for the ICG to dissipate from the field as this may take up to 20-30 minutes due to its high level of albumin binding.

At the completion of the observation period with ICG, the microscope will be removed and sterilized between uses. This would complete the observation period, which is anticipated to take 15 - 20 minutes total time. The observation will take place during the course of standard surgery and is not anticipated to delay or significantly lengthen the duration of the procedure. For example, other portions of the procedure will be continued during the observation period (e.g., setting up the circuit required for HIPEC). The tumor implants will be removed and undergo standard pathology evaluation. The patient will recover in the PACU per standard protocol.

Technical difficulties with the microscope apparatus (e.g. malfunction of the software or structural damage to any of the microscope components) or unforeseen events during the course of surgery that are unrelated to the study intervention but that result in the termination of the surgery (e.g. adverse reaction to anesthetic prior to administration of intravital dye or hemodynamic instability from a complication of the surgery) will not be considered failures of the primary objective. In these circumstances, the subject will be considered to be off-study and be replaced with a subsequent patient.

Off-line analysis of digitally recorded live video will be performed using parameters and statistical methods that have been developed in our preclinical imaging studies.[1] Lumenal cross-sectional diameter (D) of vessels and velocity (V) of dye labeled cells will be measured in off-line observations. Wall shear rate ( $\gamma$ ) will be calculated as  $8(V \div D)$ .[92] Vessel density will be determined by measuring the calculated blood vessel area as a percent of the total visual field area. If visible, the uptake of fluorescein or ICG will be measured as a diffusion rate (distance from tumor vessel over time) and as a percent of the total tumor field observed (percent of visual field expressed as surface area with dye detected). Blood flow velocity will be determined by the equation  $Q = (RBC \text{ velocity}/1.6) \times (d/2) \times \pi$ .

These data will be calculated and recorded in a spread sheet that will also be saved onto a password-protected hard drive in the Principal Investigator's laboratory. Additionally, all data will be de-identified and provided to the Biostatistician. Generated data and the raw video images will be stored for review at any time to satisfy any audit of the collected data. This saved data will readily allow the determination of a successful observation including the identification of tumor vessels, the associated vessel measurements, vessel density, and dye enhanced imaging acquisition.

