## 1.2 DIAGNOSTIC INTERVENTION - FLUORESCEIN

Drug Information - Fluorescein is delivered intravenously during the course of this observation. Fluorescein is an FDA approved drug for visual angiography. The package insert is shown in Appendix A. A single dose consists of a 5 mL vial of 25% fluorescein and costs \$3.90.

Fluorescein has a very rare incidence of anaphylactic reaction (1 in 222,000), but a skin-prick test may allow these patients to be recognized.[21] Therefore, any reported sensitivity to fluorescein will be considered an exclusion criteria as well as a positive skin-prick test performed during the routine preoperative visit (at least 1 week prior to surgery). The skin-prick test will be performed at the time of the preoperative visit if the patient decides to enter the clinical trial and signs the informed consent. Patients that are not eligible for the study or do not give consent to participate in the study will not undergo a skin-prick test.

The skin-prick test will be performed by the Principal Investigator using a sterile Duotip® lancet (Lincoln Medical, USA) in 3 separate areas of skin on the forearm. The skin-pricks will include 4 microliters of 10% fluorescein, histamine chloride (10 mg/ml) [positive control], and 50% saline solution [negative control] administered in areas of skin prepped with an alcohol pad. After 30 minutes, the appearance of a wheal greater than 3 mm in diameter is considered a positive test result in the context of the appropriate positive and negative control. If a positive test is noted, the patient will no longer be eligible for this study. For comfort and relief of any skin irritation/pruritis, the patient will be offered an anti-histamine (fexofenadine [Allegra®] 30 mg po x 1) following the skin-prick test if necessary.

The package insert for fluorescein (which is a commonly used agent in the OR and readily available to the anesthesiologist in their PYXIS system and does not require delivery from pharmacy or an order to pharmacy) is attached in the Appendix section.

The fluorescein will be provided by the study. It will be ordered and sent to surgery for the patient at the time of the planned microscopic observation.

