### **1.2.1 PRECLINICAL STUDIES WITH FLUORESCEIN**

Murine tumors have been investigated with the use of intravital microscopy in an attempt to evaluate blood vessel characteristics, blood flow patterns, and interactions with immune cell subsets.[1, 7, 9] Fluorescein conjugated to Dextran has been employed for several intravital microscopy studies[1, 22] and allows for a more precise assessment of the tumor vasculature[1, 7].

Preclinical laboratory studies have established that fluorescein can be used to image the microvasculature in B16 mouse melanoma tumors in the similar doses used clinically. Fluorescein is not expected to have a direct intervention on tumor biology. The ability to study tumor microvasculature by using IVM does not require a window chamber, and human IVM techniques have provided highly reproducible and consistent measurements. There have been several published animal studies which have demonstrated IVM of the lymphatic system in addition to blood vessels.[10, 23]

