### **1.2.2 CLINICAL STUDIES WITH FLUORESCEIN**

This protocol intends to apply the commonly used intraoperative fluorescent agent, fluorescein, to further characterize blood vessels associated with peritoneal carcinomatosis during the course of CRS-HIPEC. It is anticipated that fluorescein will be readily detectable in the microscopic field of observation following intravenous fluorescein injection. This is expected to be similar to a previous trial NCT01886235, which utilized fluorescein to study the microvasculature of melanoma primary tumors, and an on-going trial that uses fluorescein to visualize vessels associated with sentinel lymph nodes (NCT02857374).

Fluorescein is not expected to have a direct intervention on tumor biology. Fluorescein is routinely used during the course of surgery for a variety of indications (e.g. intraoperative assessment of bowel or organ perfusion, vessel angiography of the retina) and is deemed non-toxic with no long term side effects.

Clinically, fluorescein is most commonly used for ophthalmologic procedures including fluorescein angiography with intravenous injection. Fluorescein angiography is performed by injecting fluorescein sodium dye as a bolus into a peripheral vein. The normal adult dosage is 500 mg, and is typically packaged in doses of 5 mL of 10% or 2 mL of 25%. For pediatric patients, the dose is adjusted to 35 mg per 10 pounds of body weight.[24]

Upon entering the circulation, approximately 80% of the dye molecules bind to plasma proteins, which significantly reduces fluorescence because the free electrons that form this chemical bond are subsequently unavailable for excitation.[25] The remaining unbound or free fluorescein molecules fluoresce when excited with light of the appropriate wavelength. With a molecular weight of 376, fluorescein diffuses freely out of all capillaries except those of the central nervous system, including the retina.

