The dye is metabolized by the kidneys and is eliminated through the urine within 24 to 36 hours of administration. During this period of metabolism and elimination, fluorescein has the potential to interfere with clinical laboratory tests that use fluorescence as a diagnostic marker.[26, 27] To avoid any false readings, it may be prudent to schedule clinical lab tests either before the angiogram, or postpone testing for 1 or 2 days to allow sufficient elimination of the dye. Side effects of intravenous fluorescein include discoloration of the urine for 24 to 36 hours and a slight yellow skin discoloration that fades within a few hours. Nursing mothers should be cautioned that fluorescein is also excreted in human milk,[28] for this reason, nursing mothers will be excluded from this study.

Use of fluorescein sodium may be contraindicated in patients with history of allergic hypersensitivity to fluorescein. Although generally considered safe for patients receiving dialysis, one manufacturer of fluorescein suggests using half the normal dose in dialyzed patients.[29] There are no known risks or adverse reactions associated with pregnancy, but most practitioners avoid performing fluorescein angiography in pregnant women, especially in their first trimester.[30-32]

Historically, adverse reactions occur in 5% - 10% of patients and range from mild to severe.[33-39] Anecdotal evidence suggests a lower incidence of reaction in recent years and the first large study conducted in over a decade seems to confirm that, reporting a frequency of adverse reaction of just over 1%. [40] Continued improvements in manufacturing processes and implementation of tighter pharmacopeial standards are credited with this reduction and may lead to lower rates of reaction in the future.[41]

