**AK-FLUOR® (fluorescein injection, USP)**

		PRESERVATIVE FREE	RSS Barcoded	UPC Barcoded
NDC #	DESCRIPTION	SIZE	UNIT OF SALE	ORANGE BOOK CODE
17478-253-10	10% Single-dose Vial	5 mL	12	AP
17478-250-20	25% Single-dose Vial	2 mL	12	AP

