**EACH mL CONTAINS:**

ACTIVE:	17478-253-10: Fluorescein Sodium (equivalent to Fluorescein 10% w/v, 100 mg/mL); 17478-250-20: Fluorescein Sodium (equivalent to Fluorescein 25% w/v, 250 mg/mL);
PRESERVATIVE:	None;
INACTIVES:	Sodium Hydroxide and/or Hydrochloric Acid may be used to adjust pH (8.3 to 9.8), and Water for Injection.
STORAGE:	Store at 20° to 25°C (68° to 77°F). Do not freeze.

NDC #	CARDINAL	AMERISOURCEBERGEN	MCKESSON	MORRIS DICKSON
17478-253-10	2119436	861-005	2772069	084699
17478-250-20	2119444	089-829	1257831	TBA

Scan with  
smart phone  
to visit  
akorn.com

To order products call **[contact]** or [contact]** • [www.akorn.com](http://www.akorn.com)  
NOT FOR PRESCRIBING PURPOSES. PLEASE REFER TO PACKAGE INSERT FOR FULL PRESCRIBING INFORMATION.

[name]

P343 Rev. 10/13

Version 2.0, 15 March 2018

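### The fluorescein instruction (5 mL of 25%, which is 1250 mg) is 2.5 times the 500 mg adult dose the protocol cites, matches neither vial in Appendix A, and is not justified

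*Combined protocol and SAP*

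**What the plan says.** Two sections set the fluorescein dose, and they agree with each other. Section 4.2, the operative instruction, says "1 ampule (5 mL) 25% fluorescein will be injected intravenously". Section 1.2, under drug information, says "A single dose consists of a 5 mL vial of 25% fluorescein".

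Two other places describe the drug differently:

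- Section 1.2.2 gives the only adult dose in the document: "The normal adult dosage is 500 mg, and is typically packaged in doses of 5 mL of 10% or 2 mL of 25" (per cent). For children it adds that "the dose is adjusted to 35 mg per 10 pounds of body weight".
- Appendix A lists two presentations, a 10% vial of 5 mL and a "25% Single-dose Vial" of 2 mL. It defines the stronger product as "equivalent to Fluorescein 25% w/v, 250 mg/mL" and the weaker one as 100 mg/mL.

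On rationale, Section 1.2.1 says that the microvasculature was imaged "in B16 mouse melanoma tumors in the similar doses used clinically", without a figure in mg. Section 1.2.2 points to earlier human trials with fluorescein and gives no dose for them. Section 1.3 rates the risk of a reaction as low, relying on the preceding description.

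**The concern.** The instructed 5 mL at 25% is not a combination that the protocol's own dosing text or product sheet contains. It looks as if the volume of the 10% vial was written next to the concentration of the 2 mL vial. If the larger amount is deliberate, the protocol gives no reason for it. By contrast, Section 1.4 argues the 5 mg dose of indocyanine green (ICG) against a stated maximum and against doses used in vessel studies.

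Every subject, up to 30, is to receive this drug intravenously. The wording also supports two different doses. With the listed products, one ampule delivers 500 mg, while 5 mL at 25% delivers 1250 mg. Section 1.2 says the drug is on hand to the anesthesiologist without a pharmacy order, and also that it will be ordered and sent to surgery, so a pharmacy check cannot be assumed to catch the discrepancy.

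There is a smaller consequence for the data. The primary endpoint requires fluorescein to be seen in the vessels and its tissue penetration to be calculated. If the dose is read differently from case to case, the dye input to those measurements is not standardized. The documents give no dose-to-signal data, so the size of that effect is unknown.

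**Working it through.** **Inputs**

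- Instructed dose: 5 mL at 25% (Sections 1.2 and 4.2).
- Cited adult dose: 500 mg (Section 1.2.2).
- Concentrations: 10% = 100 mg/mL, 25% = 250 mg/mL (Appendix A).
- Listed vials: 5 mL at 10%, 2 mL at 25% (Appendix A).

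**Formula:** dose (mg) = volume (mL) × concentration (mg/mL).

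**Step 1. Reproduce the cited 500 mg.**

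- 5 mL × 100 mg/mL = 500 mg.
- 2 mL × 250 mg/mL = 500 mg.

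Both packagings give the cited figure exactly, so Section 1.2.2 and Appendix A are consistent.

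**Step 2. Compute the instructed dose.**

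- 5 mL × 250 mg/mL = 1250 mg.
- Ratio: 1250 / 500 = 2.5.
- Excess: 1250 − 500 = 750 mg per subject.

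**Step 3. Compare with the listed products.**

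- 5 mL / 2 mL = 2.5 vials of the 25% product, so three would have to be opened.
- One vial of either type holds 500 mg. No listed unit holds 5 mL at 25%.

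**Step 4. Express the dose by body weight.** The weights are assumed; the documents give none.

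| Weight | 500 mg | 1250 mg |
|---|---|---|
| 50 kg | 10.0 mg/kg | 25.0 mg/kg |
| 70 kg | 7.1 mg/kg | 17.9 mg/kg |
| 100 kg | 5.0 mg/kg | 12.5 mg/kg |

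The only weight-based rate in the protocol is the pediatric one, 35 mg per 10 lb or 3.5 mg/lb. It gives 500 mg at 500 / 3.5 = 143 lb (65 kg) and reaches 1250 mg only at 1250 / 3.5 = 357 lb (162 kg). This is a plausibility check and not an adult limit.

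**Step 5. Look for a justification.** No section states 1250 mg, says that the dose exceeds 500 mg, or gives a reason. The preclinical remark in Section 1.2.1 refers to doses like those used clinically, which does not support exceeding the cited clinical dose.

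**The case against.** The strongest reply is that the 500 mg figure appears in a paragraph on ophthalmic angiography, whereas this trial images peritoneal implants during surgery. The documents give no dose for that use and no maximum, and two sections agree on 5 mL at 25%. On this reading the larger dose may be intended, perhaps carried over from the earlier trials, and 500 mg is the wrong comparator. The ophthalmic context and the missing maximum are correct as stated. However, 500 mg is the only adult dose the protocol cites, and agreement between two sections may simply be copied text. If the dose is deliberate, the missing justification is itself the defect.

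Other limits should be accepted:

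- Section 1.2.2 says "Historically, adverse reactions occur in 5% - 10% of patients and range from mild to severe", and just over 1% in a more recent study, but ties neither rate to a dose. The rates therefore do not show that 500 mg is safe and 1250 mg is not.
- Section 1.2.2 links nausea to dye volume and injection rate. The instructed 5 mL is the same volume as the listed 10% vial, so that remark does not count against it.
- Appendix A as supplied is one manufacturer's product sheet. It shows that the listed vials do not match, not that a 5 mL unit at 25% is unavailable.
- Some pages and the full prescribing information were not available, so the absence of a justification is established only for the text at hand.

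None of this reconciles the instruction with the protocol's own dosing statement.

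**Conclusion.** The concern holds. The instruction amounts to 1250 mg against a cited adult dose of 500 mg: 2.5-fold, or 750 mg more per subject, for up to 30 subjects. It corresponds to neither listed vial and is unexplained. The result rests only on the concentrations in Appendix A and on multiplication. The mg/kg figures alone depend on assumed weights.

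The documents do not establish that 1250 mg breaches a limit or causes harm. They also cannot separate a transcription error from a deliberate choice. Because this is the operative instruction for an intravenous drug, it must be corrected or justified before it is relied on.

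**What to change.** First have the clinical and pharmacy leads confirm the intended dose. Then amend Sections 1.2 and 4.2 together so that each states the dose in mg with a volume and concentration that agree.

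- **If the wording was a slip:** state 500 mg, given as 5 mL at 10% or 2 mL at 25%, and name which product is used.
- **If 1250 mg is intended:** add a justification to Section 1.2. Section 1.3 should then say that the only adult dose cited is 500 mg and that the quoted reaction rates are not stated for 1250 mg.

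In either case, check the anesthesia and pharmacy order wording and the consent form against the amended text.

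The cost is a text amendment and those checks. Sample size and planned analyses do not change. If subjects have already been imaged at 1250 mg, a move to 500 mg would alter the dye load behind the visualization and penetration criteria, so the dose actually given should be recorded for each subject.

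A separate, minor point can go in the same amendment. Section 1.4 says the ICG dose will be worked out from body weight, yet Sections 1.4 and 4.2 fix it at 5 mg. Delete the weight-based sentence.
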